3.1 SYNOPSIS

Trial Title Trial Centres	A clinical trial to determine the safety, tolerability and immunogenicity of the candidate Mycobacterium avium subspecies paratuberculosis (MAP) vaccine ChAdOx2 HAV and MVA HAV in patients with active Crohn's disease Guy's and St Thomas' NHS Foundation Trust, [name]
Trial Identifier	HAV002
Clinical phase	Ib
Design	Open label, dose escalation, heterologous prime-boost study
Population	Patients with active Crohn's disease aged 18 – 50
Planned Sample Size	Participants receiving ChAdOx2 HAV will be recruited and vaccinated 6 per group, with the usual lead in for each group, up to a maximum of 12 Participants receiving MVA HAV only (n=6) will be recruited into 2 groups. A total of 10 participants will be recruited into a prime-boost group with ChAdOx2 HAV-MVA HAV Maximum possible sample size for study (n=28)
Follow-up duration	20 weeks for participants receiving ChAdOx2 HAV only 12 weeks for participants receiving MVA HAV only 20 weeks for participants receiving ChAdOx2 HAV and MVA HAV
Primary Objectives	To assess the safety and tolerability of ChAdOx2 HAV and MVA HAV in patients with active Crohn's disease administered alone and in a prime-boost regimen
Secondary Objectives	To assess the immunogenicity of ChAdOx2 HAV and MVA HAV in patients with active Crohn's disease administered alone and in a prime-boost regimen
Investigational	ChAdOx2 HAV - Viral vectored vaccine using a chimpanzee
Product	adenovirus as a vector encoding a Mycobacterium avium subspecies paratuberculosis (MAP) insert designated HAV
	MVA HAV - Viral vectored vaccine using a modified vaccinia

	Ankara as a vector encoding a Mycobacterium avium subspecies paratuberculosis (MAP) insert designated HAV
Finished products and doses	1. ChAdOx2 HAV at 2.5 x 10 ¹⁰ vp
r misrica products and doses	2. ChAdOx2 HAV at 5 x 10 ¹⁰ vp
	3. MVA HAV at 5 x 10 ⁷ pfu
	4. MVA HAV at 2 x 10 ⁸ pfu
Form	Liquid
Route	Intramuscularly (IM) into the deltoid region of the arm

3.2 Principal research objectives to be addressed

To determine the safety, tolerability and immunogenicity of the candidate Mycobacterium avium subspecies paratuberculosis (MAP) vaccine ChAdOx2 HAV and MVA HAV in patients with active Crohn's disease

3.2.1 Primary objective

To assess the safety and tolerability of ChAdOx2 HAV and MVA HAV in patients with active Crohn's disease on no current immunosuppressive therapy when administered alone and in a prime-boost regimen.

3.2.2 Primary outcome measures

To define the Maximum Tolerated Dose (MTD) of ChAdOx2 HAV and MVA HAV in patients with active Crohn's disease on no current immunosuppressive therapy when administered alone and in a prime-boost regimen. The definition of MTD is defined as per the Group Holding Rules in section 3.2.3.

The following parameters will be used to assess response and safety for all study groups:

- Occurrence of local reactogenicity signs and symptoms for 7 days following the vaccination
- Occurrence of systemic reactogenicity signs and symptoms for 7 days following the vaccination
- Occurrence of adverse events for 28 days following the vaccination
- Change from baseline for safety laboratory measures
- Occurrence of serious adverse events during the whole study duration

Participants in groups 1-2 will undergo clinical follow up for a further 20 weeks following completion of the vaccination regimen. SAEs will be collected throughout the study.

Participants in groups 3-4 will undergo clinical follow-up for a further 12 weeks following completion of the vaccination regimen. SAEs will be collected throughout the study. Participants in group 5 will undergo clinical follow-up for a further 20 weeks following completion of the vaccination regimen. The duration of follow up reflects the desire to obtain sufficient safety data with the first use of ChAdOx2 HAV, MVA HAV and a prime-boost regimen with ChAdOx2 HAV-MVA HAV in humans with Crohn's Disease. Considering the pre-existing safety data on several other MVA based constructs, participants receiving MVA HAV will be followed by a shorter period.

3.2.3 Group holding rules

For safety reasons the first participant to receive a new vaccine dose will be vaccinated alone and we will wait 48 hours before vaccinating subsequent participants. Two further participants may be vaccinated 48 hours after the first, and then at least another 48 hours gap will be left before vaccinating the rest of the participants receiving that dose of vaccine.

If the first three 2.5×10^{10} vp doses are deemed safe (none of the first three participants experiences a Grade 3 severe adverse reaction lasting more than 48 hours), the first patient in the higher dose of 5×10^{10} vp will be vaccinated at the same time as the remaining 3 at the lower dose. Two further participants may be vaccinated at the higher dose, 48 hours after the first, and then at least another 48 hours gap will be left before vaccinating the rest of the participants at the 5×10^{10} vp dose.

If 2 or more participants in groups 1-2 experience Grade 3 severe adverse reactions lasting more than 48 hours at a given dose, then no further participants will be vaccinated at that dose or a higher dose and the previously tolerated dose will be recorded as the Maximum Tolerated Dose (MTD).

The group holding rules are as follows (groups 1-5)

Solicited local adverse events:

 If 2 vaccinations in a group are followed by the same Grade 3 solicited local adverse event beginning within 2 days after vaccination (day of vaccination and one subsequent day) and persisting at Grade 3 for >48 hrs.

Solicited systemic adverse events:

 If 2 vaccinations in a group are followed by the same Grade 3 solicited systemic adverse event beginning within 2 days after vaccination (day of vaccination and one subsequent day) and persisting at Grade 3 for >48 hrs.

Unsolicited adverse events:

 If 2 vaccinations in a group are followed by the same Grade 3 unsolicited adverse event beginning within 7 days after vaccination that is considered related to vaccination and persists at Grade 3 for >48 hrs.

• Laboratory adverse event:

- If 2 vaccinations in a group are followed by the same Grade 3 laboratory adverse event beginning within 7 days after vaccination and persists at Grade 3 for >72 hrs.
- A serious adverse event considered possibly, probably or definitely related to vaccination occurs
- Death occurs
- A life-threatening reaction occurs

If a holding rule has been met and following an internal safety review it is deemed appropriate to restart dosing, a request to restart dosing with pertinent data must be submitted to the regulatory authority as a request for a substantial amendment. The internal safety review will consider:

- The relationship of the AE or SAE to the vaccine.
- The relationship of the AE or SAE to the vaccine dose, or other possible causes of the event.
- If appropriate, additional screening or laboratory testing for other participants to identify those who may develop similar symptoms and alterations to the current Participant Information Sheet (PIS) are discussed.
- New, relevant safety information from ongoing research programs on the various components of the vaccine.

The UK Competent Authority (MHRA) and approving Research Ethics Committee will be notified if the trial is terminated early.

All vaccinated participants will be followed for safety until the end of their planned participation in the study or until resolution or stabilisation (if determined to be chronic sequelae) of their AEs, providing they consent to this.

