4.4 First participants

The first participant in Group 1 will be vaccinated alone and then reviewed 48 hours following vaccination. The chief investigator (CI) and the chair of the Safety Review Committee (SRC) will be asked to provide the decision on whether to proceed after the safety review of the first participant. If there are no safety concerns, another two Group 1 participants will be vaccinated at least one hour apart, and reviewed in a further 48 hours. The CI and the chair of the SRC will be asked to provide the decision on whether to proceed with the vaccination of a further 3 participants in Group 1 and 1 participant in Group 2 following safety review of the previous vaccinated participants. This review will include the results of safety blood tests at day 7 post vaccination.

The same procedure will apply for the first participant in Group 2. He/she will be vaccinated ahead of the other participants. The profile of adverse events from that participant will be examined and no other participants will be vaccinated until at least 48 hours have elapsed following this participant being vaccinated.

The first participant in group 3 will be vaccinated alone and then reviewed 48 hours following vaccination. The chief investigator (CI) and the chair of the Safety Review Committee will be asked to provide the decision on whether to proceed after the safety review of the first participant. If there are no safety concerns, another two Group 3 participants may be vaccinated at least one hour apart, and reviewed in a further 48 hours. The CI and the chair of the SRC will be asked to provide the decision on whether to proceed with vaccination at the next highest dose following safety review of the previous vaccinated participants. This review will include the results of safety blood tests at day 7 post vaccination.

The first participant in group 4 will be vaccinated alone and then reviewed 48 hours following vaccination. The chief investigator (CI) and the chair of the Safety Review Committee will be asked to provide the decision on whether to proceed after the safety review of the first participant. If there are no safety concerns, another two Group 4 participants may be vaccinated at least one hour apart, and reviewed in a further 48 hours. After 3 subjects in group 4 have been vaccinated and followed up for 7 days, an interim safety review will be performed.

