4.6 Sequence of Enrolment and Vaccination of Participants (groups 1 and 2)

The first participant in Group 1 will be vaccinated alone and then reviewed 48 hours following vaccination. The chief investigator (CI) and the chair of the Safety Review Committee will be asked to provide the decision on whether to proceed after the safety review of the first participant. If there are no safety concerns, another two Group 1 participants will be vaccinated at least one hour apart, and reviewed in a further 48 hours. The CI and the chair of the SRC will be asked to provide the decision on whether to proceed with the vaccination of a further 3 participants in Group 1 and 1 participant in Group 2 following safety review of the previous vaccinated participants. This review will include the results of safety blood tests at day 7 post vaccination.

The same procedure will apply for the first participant in Group 2. He/she will be vaccinated ahead of the other participants. The profile of adverse events from that participant will be examined and no other participants will be vaccinated until at least 48 hours have elapsed following this participant being vaccinated.

Therefore, the possible numbers of participants to be vaccinated, assuming the adverse event profile allows progression to the high dose is 6 in each group. All participants will be issued with the telephone number of the investigator and encouraged to contact the investigators if there are any problems.

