6.3 Statistical considerations

Time points

The primary outcome is measured across all follow-up time period (2 or more participants experiencing Grade 3 severe adverse reactions (SAR) lasting more than 48 hrs). Secondary outcomes are presented using descriptive statistics for baseline and follow-up timepoints. Data will be presented using descriptive statistics and no repeated measures analysis will be conducted.

Stratification and clustering

There will be no stratification or clustering

Missing baseline data

Individuals must have all baseline measurements as part of screening and as standard of care. This data will not be imputed for the primary analysis.

Missing outcome data

Individuals will be monitored for the entire followup duration and thus there will be no missing data for the primary outcome. If data is missing for the secondary or exploratory outcomes analysis will be carried out on a complete case basis with no imputation.

Method for handling multiple comparisons

Bonferroni adjustment for multiple comparisons will be used.

Method for handling non-compliance (per protocol/CACE analyses)
Since this is a single arm trial CACE analysis is not possible

Model assumption checks

Only descriptive statistics will be presented for all outcomes and thus no model assumption checks are needed. As the sample size is small, medians and IQRs will be presented instead of means and standard deviations.

Sensitivity analyses

No sensitivity analyses are planned

Planned subgroup analyses

No subgroup analyses are planned

Interim analysis

Interim safety reviews are planned after vaccinating the first participants in all groups, and prior to moving up a dose. The safety reviews are summarized in the table below, and described in more detail in section 4.4 to 4.7

Safety reviews

Table 7 Planned interim safety reviews

Interim safety	When
review	
1	After vaccination of the first participant in
	Group 1
2	After vaccination of the participant 2 and 3
	in Group 1, and prior to vaccinating
	participants 4-6 in Group 1 and participant
	1 in Group 2
3	After vaccination of the first participant in
	Group 2
4	After vaccination of the first participant in
	Group 3
5	After vaccination of the participant 2 and 3
	in Group 3, and prior to vaccinating the first
	participant in Group 4
6	After vaccination of the participant 2 and 3
	in Group 4, and prior to vaccinating the first

	participant in Group 5
--	------------------------

7 Software

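### At the minimum spacing allowed in Group 2, the two-participant stopping rule cannot act before participants 4–6 are dosed, and the SAP lists no review at that step

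*SAP*

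**What the plan says.** **Spacing.** For the higher ChAdOx2 dose, section 3.2.3 states: "Two further participants may be vaccinated at the higher dose, 48 hours after the first, and then at least another 48 hours gap" before the rest of the group. The same 48 + 48 hour pattern is set there for any new dose.

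**Stopping rule.** The same section applies "If 2 or more participants in groups 1-2 experience Grade 3 severe adverse reactions lasting more than 48 hours at a given dose". Dosing at that level or above then ends, and the previous dose becomes the maximum tolerated dose (MTD). The separate holding rules for solicited events require the same event after two vaccinations, "beginning within 2 days after vaccination (day of vaccination and one subsequent day) and persisting at Grade 3 for >48 hrs".

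**Reviews, Group 1.** Under sections 4.4 and 4.6, the chief investigator and the chair of the Safety Review Committee decide whether to "proceed with the vaccination of a further 3 participants in Group 1 and 1 participant in Group 2 following safety review" of those already dosed. On its content, section 4.4 adds: "This review will include the results of safety blood tests at day 7 post vaccination".

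**Reviews, Group 2.** Section 4.6 says "The same procedure will apply for the first participant in Group 2", and then specifies only a 48-hour wait after that one person. Section 6.3 gives the general scheme: "Interim safety reviews are planned after vaccinating the first participants in all groups, and prior to moving up a dose". Table 7 has an entry worded "After vaccination of the participant 2 and 3" for Groups 1, 3 and 4. Group 2 has only review 3, after its first participant; review 4 already concerns Group 3.

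**The concern.** A rule that halts dosing after two qualifying reactions exists to limit how many people receive a poorly tolerated dose. It can do so only if at least two of those already dosed have been followed long enough to qualify. In Group 2 the required duration (more than 48 hours) is longer than the minimum follow-up of participants 2 and 3 (48 hours), and the SAP lists no review that would force a longer wait. Participants 4–6 at the higher dose could therefore be vaccinated while the rule is still unable to act. At the lower dose, participants 4–6 wait for a review of participants 1–3 with day-7 results.

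**Working it through.** The SAP gives no operating characteristics for the rule, so there is no stated figure to reproduce.

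**1. Follow-up at the minimum spacing (section 3.2.3)**

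| Participant | Dosed at | Follow-up at 96 h | Latest onset that can be recognised as lasting more than 48 h |
|---|---|---|---|
| 1 | 0 h | 96 h | before 96 − 48 = 48 h |
| 2 | 48 h | 48 h | none (48 − 48 = 0 h) |
| 3 | 48 h | 48 h | none |

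One of three participants is assessable, against a threshold of two. The solicited-event holding rules use the same persistence and also need two cases, so they cannot act either.

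*Edge case.* Suppose participants 2 and 3 are dosed one hour apart, as stated for Group 1, and the gap runs from participant 3 (0, 48, 49, then 97 h). Participant 2 then has 49 h of follow-up, so a reaction starting in the first hour could just qualify.

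**2. Chance that the rule can act before participants 4–6**

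Assumptions: each participant has a qualifying event with probability p, independently; onset is uniform over 0–48 h, the solicited window in section 3.2.3. The values of p are illustrative.

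The fraction of events recognisable after t hours is F(t) = min(1, max(0, (t − 48)/48)). With gap g after participants 2–3, participant 1 has F(g + 48) and participants 2–3 have F(g).

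- g = 48 h: F = 1, 0, 0, so P(2 or more) = 0.
- g = 48 h with the one-hour stagger: F(49) = 1/48 for participant 2, so P = p²/48.
- g = 72 h: F = 1, 0.5, 0.5. With q = p/2, P = q² + 2q(1 − q)p. At p = 0.2: 0.01 + 2 × 0.1 × 0.9 × 0.2 = 0.046.
- g = 96 h, or a day-7 review: F = 1, 1, 1, so P = 3p²(1 − p) + p³. At p = 0.2: 0.096 + 0.008 = 0.104.
- Participants spared on average, compared with the minimum: 3P. At p = 0.2: 3 × 0.104 = 0.31.

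| Assumed p | 5% | 10% | 20% | 30% | 40% | 50% |
|---|---|---|---|---|---|---|
| Gap 48 h (permitted minimum) | 0 | 0 | 0 | 0 | 0 | 0 |
| Gap 72 h | 0.3% | 1.2% | 4.6% | 9.9% | 16.8% | 25.0% |
| Gap 96 h or day-7 review | 0.7% | 2.8% | 10.4% | 21.6% | 35.2% | 50.0% |
| Spared at 96 h or day 7 | 0.02 | 0.08 | 0.31 | 0.65 | 1.06 | 1.50 |

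The staggered 48-hour case runs from 0.05²/48 = 0.005% to 0.5²/48 = 0.5%.

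**3. Sensitivity to onset time.** If all onsets fall uniformly in the first 24 h, a 72-hour gap already gives the 96-hour values, and the 48-hour gap still gives zero. If some onsets come after 48 h, the 96-hour values are upper bounds.

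**4. Earliest dosing of participants 4–6, counted from the first Group 2 dose.** Now: 48 + 48 = 96 h. With a 96-hour gap: 48 + 96 = 144 h. With day-7 data on participants 2–3: 48 + 168 = 216 h, or 192 to 240 h with the one-day visit window.

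**The case against.** The strongest objection is that dosing order and review points belong to the protocol. Section 4 of the SAP refers to protocol section 8.4.2.2, which is not at hand and may contain the missing review. The SAP is also consistent with its own scheme: reviews follow first participants and precede a dose increase, and Group 2 is the top ChAdOx2 dose, so there is no increase to review. The 48 hours is a floor, and the sponsor may wait longer or dose participants 4–6 one at a time. A day-2 visit with adverse-event ascertainment and bloods would normally show an ongoing Grade 3 reaction. A single related serious adverse event, a death or a life-threatening reaction triggers a hold at any time. The model borrows its onset window from the solicited-event rules, whereas the MTD rule has none, and the larger gains need event rates that nothing in the SAP supports.

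Much of this stands as a limit on size. It does not remove the mismatch. The SAP itself fixes both the spacing and the rule, and the two do not fit at the spacing it allows. It does not make a Grade 3 reaction of less than 48 hours seen on day 2 a reason to hold. The other holds cover different events from the non-serious Grade 3 reactions that the two-participant rule addresses. Nor are first-three reviews confined to dose increases: Table 7 has one after Group 4 participants 2 and 3, before Group 5, which section 4.7 plans at the same MVA HAV dose.

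**Conclusion.** The point holds. With Group 2 dosed at the 0/48/96-hour minimum, the two-participant rule has no chance of acting before participants 4–6 are exposed, apart from the first-hour edge case (0.5% at most over the rates assumed). The SAP lists no review that closes the gap. The zero at the minimum follows from the timing alone and needs no event rate.

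The benefit of correcting it does depend on the assumed rate and onset model. It is small at a true rate of 10% or less (0.08 participants spared or fewer) and grows if the dose is poorly tolerated. The consequence is avoidable exposure of up to three patients. The final MTD determination is unaffected, because two qualifying reactions in Group 2 give the same MTD whether or not participants 4–6 were dosed. The point should be fixed because the change is cheap. Whether the protocol already contains such a review could not be checked.

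**What to change.** In sections 3.2.3, 4.4 and 4.6, require a review of Group 2 participants 1–3, including day-7 data, before participants 4–6 are vaccinated, as is done in Group 1. Add it to Table 7 as a row between reviews 3 and 4, and align the wording with protocol section 8.4.2.2.

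The minimum alternative is to lengthen the gap after participants 2–3 from 48 to at least 96 hours (2-day onset window plus 48 hours' persistence). The day-7 option is better because it uses an existing visit and blood test. Day 4 falls between the scheduled day-2 and day-7 visits, so the 96-hour option would need a telephone check or rely on participants' own reports. Neither option captures every unsolicited or laboratory event with onset up to day 7; those remain under the ongoing holding rules.

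Cost: participants 4–6 are dosed about 5 days later with the day-7 option (4 to 6 days with the visit window), or 2 days later with the 96-hour option. The SAP needs wording in three sections and one table row, and the protocol needs matching text if it lacks this review. The day-7 option adds no visit, and no analysis changes.

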3.3 Secondary objective

To assess the immunogenicity and clinical response of ChAdOx2 HAV and MVA HAV in patients with active Crohn's disease on no immunosuppressive therapy when administered alone and in a prime-boost regimen.

3.3.1 Secondary outcome measures

Immunogenicity

Measures of immunogenicity may include:

ELISPOT to enumerate IFN-γ producing T cells

Other exploratory immunology may be carried out in collaboration with other specialist laboratories. This would involve transfer of serum/plasma and/or peripheral blood mononuclear cells (PBMC), but samples would be anonymised. Participants will be consented for this.

Sampling of exploratory immunology responses

20ml of whole blood will be taken at baseline (D0) and days 28 and 56 (groups 1 and 2). For Group 5 10ml of whole blood will be taken at screening, with 30ml taken at baseline (D0) and days 56 and 112 and an additional 20ml on days 28 and 84 of the study for use in assays to measure immune responses of various types to the vaccine.

Assessment of clinical response

All participants will undergo an evaluation of Crohn's disease activity at screening and at day 56 for groups 1-4. Group 5 will undergo an evaluation of Crohn's disease activity at screening, on day 56 and again on day 112. For Group 5, endoscopic scoring by flexible sigmoidoscopy or colonoscopy will be undertaken by the CD-SES (simple endoscopic score) at screening and at day 112.

Exploratory immunology may be carried out in collaboration with other specialist laboratories. This would involve transfer of serum/plasma and/or peripheral blood mononuclear cells (PBMC), but samples would be anonymised. Participants will be consented for this.

4 Trial design

This is a phase Ib open-label dose escalation study to assess the safety, tolerability and immunogenicity of the candidate Mycobacterium avium subspecies

paratuberculosis (MAP) vaccine, ChAdOx2 HAV in patients with active Crohn's disease aged 18-50.

Participants will be enrolled and doses will be escalated according to a study plan which will run as outlined in section 8.4.2.2 of the protocol and summarized in the table below:

Table 1 Summary of dosing regimen

Group	Dose
1 (n=6)	ChAdOx2 HAV, 2.5x1010 vp
2 (n=6)	ChAdOx2 HAV, 5x1010 vp
3 (n=3)	MVA HAV, 5x107 pfu
4 (n=3)	MVA HAV, 2x10 ₈ pfu
5 (n=10)	Prime boost Regime (doses depended on
	the results from Groups 1-4)

